7. PLANNED ANALYSIS

All efficacy analyses will be purely exploratory in nature. The following analyses are planned at different stages throughout the trial.

- **Primary Analysis (Week 16)**

The primary analysis is planned to be performed when all patients complete week 16 visit of the trial.

A memorandum is planned to summarize the results of the primary analysis at Week 16.

- **Final analysis (Week 44)**

The analysis of the entire efficacy, safety, PK, and biomarker data collected through the full 44 weeks of follow-up will be performed once all entered patients have completed the trial (up to EoS for Non-Responders/Week 44 Visit); at that time point, a final database lock will be done and all data through week 44 will be reported. The majority of biomarkers will be reported outside the CTR.

General Remarks

The format of the listings and tables will follow the BI guideline “Standards for Reporting of Clinical Trials and Project Summaries” [BI-KMED-BDS-HTG-0045] (10) with the exception of those generated for PK.

The individual values of all patients will be listed, including those collected during the off-treatment period. Listings will generally be sorted by country, centre number, patient number and visit (if visit is applicable in the respective listing). AE listings will be sorted by treatment (see [Section 7.8.1](#) below for details).

The following standard descriptive statistical parameters will be displayed in summary tables of continuous variables:

N	number of non-missing observations
Mean	arithmetic mean
SD	standard deviation
Min	minimum
Q1	lower quartile
Median	median
Q3	upper quartile
Max	maximum

For PK analyte concentrations, the following descriptive statistics will additionally be calculated:

- CV arithmetic coefficient of variation
- gMean geometric mean
- gCV geometric coefficient of variation

The data format for descriptive statistics of concentrations will be identical with the data format of the respective concentrations.

[figure not shown]
Statistical parameters will be displayed to a defined number of decimal places as specified in the BI guideline “Standards for Reporting of Clinical Trials and Project Summaries” (10).

Tabulations of frequencies for categorical data will include all possible categories and will display the number of observations in a category as well as the percentage (%) relative to the respective treatment. Percentages will be rounded to one decimal place. The category missing will be displayed if and only if there actually are missing values. Percentages will be based on all patients in the respective patient set whether they have non-missing values or not.

Disposition of the patient population participating in the trial will be summarised by presentation of the frequency of patients screened, entered/randomised, screened but not entered, treated, entered but not treated, who completed all doses of trial medication as planned (overall, in the double-blind treatment period, and in the BI open-label treatment period), who prematurely discontinued study drug administration by reason (overall, in the double-blind treatment period, and in the BI open-label treatment period), patients still ongoing in the study, those, who completed the observational period as planned, who prematurely discontinued study participation, who completed Week 4 visit (V4), who completed the re-allocation visit at Week 16 (V7), number of patients reallocated to BI open-label treatment. Disposition will be listed by country.

The frequency of patients with iPDs will be presented for the RS by treatment. The IPDs will be listed per patient indicating whether or not the iPD led to exclusion from patient sets analysed.

The frequency of patients in each of the different analysis sets will also be presented by treatment.

7.1 DEMOGRAPHIC AND OTHER BASELINE CHARACTERISTICS

Only descriptive statistics are planned for this section of the CTR.

Descriptive statistics will be presented by treatment for demographic parameters and baseline characteristics, based on the RS.

For the continuous variables described below, categories are defined in [Table 7.1: 1](#). These variables will be presented according to the number and percentage of patients in each category.

Table 7.1: 1 Categories for summary of continuous variables

Variable	Categories
Age	< 30 years ≥ 30 years
	< 50 years 50 to < 65 years 65 to < 75 years ≥ 75 years
	< 65 years ≥ 65 years
Weight	≤70 kg >70 to ≤80 kg >80 to ≤ 90 kg >90 kg
BMI	< 25 kg/m ² 25 to < 30 kg/m ² ≥ 30 kg/m ²
Time since first diagnosis	≤ 1 year > 1 to ≤ 5 years > 5 to ≤ 10 years > 10 years
Disease severity based on EASI total score	>7 to ≤ 21 (moderate) ≥ 21 (severe)
Disease severity based on IGA score	= 3 (moderate) = 4 (severe)
Age at disease onset	≤12 years old >12 years old
	<18 years old ≥18 years old

7.2 CONCOMITANT DISEASES AND MEDICATION

Analyses of concomitant diseases and medication will be based on the RS.

Concomitant diseases will be coded according to the most recent version of MedDRA.

Concomitant medication will be coded according to the most recent version of the World Health Organisation – Drug Dictionary.

Concomitant diseases which are present at start of the study, as well as characteristics of the trial disease, will be descriptively summarized by treatment.

A medication will be considered concomitant to treatment, if it

- is ongoing at the start of trial treatment or
- starts within the on-treatment period (see [Section 6.1](#) for a definition of study analysis phases).

Concomitant medication use will be summarised with frequency and percentage of patients by ATC3 class and preferred name. Summaries will be presented for:

- historical medication taken before the first study drug administration of the double-blind period (i.e., the start and stop dates are before the date of the first study medication infusion)
- concomitant medication that started before the double-blind treatment (i.e., concomitant medication start date was prior to first study treatment administration)
- concomitant medication started and taken within the double-blind period (from the day of the first treatment administration to the date of the Week 16 visit – 1 day)
- concomitant medication that started on or after the Week 16 (V7) visit date (i.e., concomitant medication start date was on the Week 16 visit date or thereafter)

The frequency and percentage of patients with previous medication for AD will be displayed as per data collected in the eCRF (i.e., separately for topical, non-topical, and non-topical/non-drug therapies). Frequencies by preferred name and treatment arm will be displayed.

Concomitant use of non-drug therapies will be summarized with frequency and percentage. Summaries will be presented for

- historical non-drug therapies taken before the first study drug administration of the double-blind period (i.e., the start and stop dates are before the date of the first study medication infusion)
- concomitant non-drug therapies that started before the double-blind treatment (i.e., concomitant non-drug therapy start date was prior to first study treatment administration)
- concomitant non-drug therapies started and taken within the double-blind period (from the day of the first treatment administration to the date of the Week 16 visit – 1 day)
- concomitant non-drug therapies that started on or after the Week 16 (V7) visit date (i.e., concomitant non-drug therapy start date was on the Week 16 visit date or thereafter)

In addition, the frequency and percentages of patients with concomitant AD medication used during the double-blind period (i.e., starting at baseline visit or thereafter) will be displayed by ATC3 and preferred name and by treatment.

The relevance of the concomitant therapies to the evaluation of PK will be decided no later than at the RPM/DBLM.

7.3 TREATMENT COMPLIANCE

Treatment compliance will be summarised overall via total volume infused (as a % of planned) for the SAF using descriptive statistics (N, mean, SD, minimum, median, maximum). The volume infused (as a % of planned) is defined as the volume infused at a visit (in ml as recorded in the eCRF), divided by 100 ml (the volume the patient should have received).

In case the total volume administered (including saline) is greater than 100 mL (including flushing volume), 100mL i.e., full infusion will be used in the analysis.

For the patients who discontinued the study treatment prematurely only the visits on or before premature discontinuation will be used for the calculation of overall compliance.

The number and percentage of patients with the following overall compliance categories will be presented:

- "< 80% of planned",
- "80 to 100% of planned"

The number of patients who received a dose will be tabulated per visit.

7.4 PRIMARY ENDPOINT

The primary endpoint for this trial is the percentage change from baseline in EASI Score at Week 16.

7.4.1 Primary analysis of the primary endpoint

The analysis of the primary endpoint will be based on Section 7.3.1 of the CTP:

From CTP Section 7.3.1: The primary analysis is a restricted maximum likelihood (REML) based approach using a mixed model with repeated measurements (MMRM) comparing the percent change from baseline of EASI score after 16 weeks of treatment.

The analysis will include the fixed, categorical effects of treatment-by-visit interaction, stratification factor Asian/Non-Asian, and the fixed continuous effects of baseline-by-visit interaction. Visits will be treated as the repeated measure with an unstructured covariance structure used to model the within-patient measurements. The Kenward-Roger approximation will be used to estimate denominator degrees of freedom and adjust standard errors. Significance tests will be based on least-squares means using a two-sided $\alpha=0.10$ (two-sided

90% confidence intervals (CI)). The primary treatment comparison will be the contrast between treatments at Week 16.

SAS code for the above model will be based on the following structure:

```
PROC MIXED DATA=alldat cl method=reml;
  CLASS visit trt stratum subject;
  MODEL ept = base visit trt stratum visit*trt base*visit / ddfm=kr s CL;
  REPEATED visit / subject= subject type=un r rcorr;
  LSMEANS visit*trt / pdiff=all om cl alpha=0.10 slice=visit;
RUN;
```

[figure not shown]
For handling of non-convergence see [Section 9.1](#).

[figure not shown]
The following hypothesis testing will be performed having an alpha level of 10% (two-sided) or 5% (one-sided):

H_0 : Mean percent change from baseline in EASI score at Week 16 (BI 655130)
≤ Mean percent change from baseline in EASI score at Week 16 (Placebo)

H_1 : Mean percent change from baseline in EASI score at Week 16 (BI 655130)
> Mean percent change from baseline in EASI score at Week 16 (Placebo)

The primary analysis will be performed on the FAS with patients analysed according to the stratum to which they belong (regardless of any miss-assignment to treatment based on identification of the wrong stratum).

7.5 SECONDARY ENDPOINTS

7.5.1 Key secondary endpoint

This section is not applicable as no key secondary endpoint has been specified.

7.5.2 Secondary endpoints

7.5.2.1 Secondary efficacy endpoints

All secondary efficacy endpoints will be analysed on FAS.

The continuous secondary efficacy endpoints (change from baseline in EASI at Week 4 and change from baseline in SCORAD at Week 4 and 16) will be analysed using the same MMRM model as defined for the primary endpoint. Both absolute and percent change from baseline will be analysed as an outcome.

A responder analysis based on the EASI Score will be performed at Week 4 and 16.

[figure not shown]
The binary endpoints defined above will be analysed with a logistic regression model including treatment and Asian/Non-Asian as explanatory variables. Risk difference for BI655130 versus placebo will be obtained as well as the response rates for the treatment groups.

[figure not shown]
As a sensitivity analyses, the Cochran-Mantel-Haenszel (CMH) test adjusted by Asian/Non-Asian will be performed.

The proportion of patients who achieved at least a 2-grade reduction from baseline in IGA to clear (0) or almost clear (1) at Week 4 and 16 will be analysed with CMH test.

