Trial endpoints	Primary endpoint 
Percentage change from baseline in EASI at Week 16 Secondary endpoint 
Number of patients with drug related AEsAbsolute and percentage change from baseline in EASI at Week 4Proportion of patients with a 50% improvement from baseline in EASI (EASI50) at Week 4 and 16Proportion of patients with a 75% improvement from baseline in EASI (EASI75) at Week 4 and 16Change from baseline in SCORAD at Week 4 and 16Proportion of patients achieving at least a 2-grade reduction from baseline to clear (0) or almost clear (1) in IGA at Week 4 and 16
Trial design	Double-blind, randomised, placebo-controlled comparison of two groups over 16 weeks
Total number of patients randomised	Approximately 45 patients will be entered in the study
Number of patients on each treatment	30 patients in the active group 15 patients in the placebo group
Diagnosis	Adult patients with moderate to severe atopic dermatitis

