3.3.2 Inclusion criteria

1. Signed and dated written informed consent in accordance with Good Clinical Practice (GCP) and local legislation prior to the start of any screening procedures
2. Male or female patients, 18 to 75 years of age at screening
3. Diagnosis of atopic dermatitis for at least 1 year
4. Moderate to severe atopic dermatitis defined as:
 - At least 10% Body Surface Area (BSA) of atopic dermatitis involvement at screening and baseline
 - Eczema Area and Severity Index (EASI) of at least 12 at screening and at least 16 at baseline
 - Investigator Global Assessment (IGA) of at least 3 at screening and baseline
5. Documented history of inadequate response to topical corticosteroid as judged by the investigator
6. Willing to use a standard emollient for the duration of the study
7. Women of childbearing potential (WOCBP)² must be ready and able to use highly effective methods of birth control per ICH M3 (R2) that result in a low failure rate of less

² A woman is considered of childbearing potential (WOCBP), i.e. fertile, following menarche and until becoming post-menopausal unless permanently sterile.

Permanent sterilisation methods include hysterectomy, bilateral salpingectomy and bilateral oophorectomy. Tubal ligation is NOT a method of permanent sterilisation.

than 1% per year when used consistently and correctly. A list of contraception methods meeting these criteria is provided in the patient information.

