4.1.3 Method of assigning patients to treatment groups

An Interactive Response Technology (IRT) will be used to screen and randomise eligible patients, perform subsequent drug assignment, manage initial/re-supply ordering of drug supplies and handle emergency un-blinding. The investigator will receive all necessary instructions to access IRT from the Sponsor or chosen provider. Detailed IRT functions and procedures will be documented in the user requirement specifications mutually agreed to by the sponsor and the IRT vendor. Patients will be randomly assigned to one of the treatment groups through the assignment of medication which will be treatment group-specific (Section [3.1](#)). For technical and statistical features of the treatment allocation process, please see Sections [4.1.4](#) and [7.6](#).

During Visit 2 (W0) and after the patient's eligibility has been confirmed, the treatment will be assigned via IRT. Patients will be randomized to receive BI 655130 600 mg or placebo in a ratio of 2:1. The assignment will occur in a blinded fashion via IRT.

During Visit 7 (W16) patients will be evaluated with the EASI scoring system (see Section [5.1](#)) and based on the response will be reassigned via IRT to receive BI 655130 600 mg or no treatment at all. The re-assignment will occur in an open label fashion.

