7.3.2 Secondary endpoint analyses

The endpoint change from baseline in SCORAD will be analysed using the same model as used for the primary endpoint (MMRM).

For the primary endpoint variable, the EASI score, responder analyses will be performed. A patient is defined as EASI50/75 responder when percent change from baseline of the EASI score is $\geq 50\%$ or $\geq 75\%$, resulting in binary variable with values of 1 (=response) or 0 (=non-response). A logistic regression model will be used to predict the response rates and to calculate the risk difference for BI 655130 versus placebo. As a sensitivity analyses, the Cochran-Mantel-Haenszel (CMH) test adjusted by randomization stratum (Asian/Non-Asian) will be used.

For the proportion of patients with IGA 0 or 1 at weeks 4 and 16, also the CMH test will be used.

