5.2.2 Secondary endpoints

The secondary endpoints are listed below.

- Drug-related Adverse Events (AEs)

Numbers and percentages of patients with drug-related AEs will be presented.

- Change from baseline in EASI Score at Week 4

The absolute and percent change from baseline as well as the absolute values at visits will be analysed.

- EASI50/75 responders at Week 4 and 16

Numbers and percentages will be analysed.

Achievement of Decrease in EASI \geq xx% (EASIxx)

Achieving a response of xx% or larger decrease from baseline in EASI score is denoted as EASIxx. The EASIxx represents a binary variable with values of 0 (= non-response) or 1 (=response).

It is calculated based on the following approach (with xx taking a value of 50 or 75):

$$\text{If } \left\{ \frac{\text{EASI(BL)} - \text{EASI(current)}}{\text{EASI(BL)}} \times 100 \right\} \geq xx \text{ then EASIxx}=1,$$

else EASIxx = 0.

- Change from baseline in SCORing of Atopic Dermatitis (SCORAD) at Week 4 and 16

The absolute and percent change from baseline as well as the absolute values at visits will be analysed.

The SCORAD consists of three elements: extent of disease, intensity of disease, and subjective symptoms (Pruritus and Sleep Loss). It sums up to a maximum of 103 points. Two of the SCORAD items are subjective symptoms (C) assessed on Visual Analog Scales (VAS) from 0 to 10: Pruritus VAS and Sleep Loss VAS.

The following formula will be used to calculate the SCORAD element assessing the Extent of the disease:

$$\text{Extent Score}(A) = (\text{Face}_{\text{Front}} \times 4.5 + \text{Upper_Limbs}_{\text{Front}} \times 9 + \text{Trunk}_{\text{Front}} \times 18 + \text{Lower_limbs}_{\text{Front}} \times 18 + \text{Genitals}_{\text{Front}} \times 1 + \text{Head}_{\text{Back}} \times 4.5 + \text{Upper_limbs}_{\text{Back}} \times 9 + \text{Trunk}_{\text{Back}} \times 18 + \text{Lower_limbs}_{\text{Back}} \times 18) / 100$$

In the SCORAD element assessing the Intensity of the disease the following scoring will be used:

- 0 for "Absence"
- 1 for "Mild"
- 2 for "Moderate"
- 3 for "Severe"

The SCORAD Intensity score element will be derived using the formula below:

$$\text{Intensity Score}(B) = (\text{Erythema_Score} + \text{Edema/Papulation_Score} + \text{Oozing/crusts_Score} + \text{Excoriations_Score} + \text{Lichenification_Score} + \text{Dryness_Score})$$

For the SCORAD element subjective symptoms the following formula will be used:

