6.3 SUBJECT SETS ANALYSED

The following analysis sets will be defined for this trial:

- Enrolled set (ES)
This patient set includes all patients who signed informed consent. It will be used for display of patient disposition.
- Randomized set (RS)
This patient set includes all patients who were randomized into the trial. It will be used for display of patient disposition, baseline and demographic characteristics, and patients with IPDs.
- Safety analysis set (SAF)
This patient set includes all randomized patients who received at least one dose of study drug. It will be the main analysis set for presentation of safety. Treatment assignment will be based on the actual treatment administered. Actual treatment refers to the actual treatment administered at the first dosing. This treatment should be followed through the whole trial, regardless of the initially randomised treatment.

- Safety analysis set in the open-label treatment period (SAF-OL)
This patient set includes all randomized patients who received at least one dose of study drug and received study medication after re-allocation visit (i.e., after Week 16 visit). Treatment assignment will be based on the actual treatment administered starting from Week 16 visit. This analysis set will be the main set for presentation of the safety data for the treatment re-allocation period.
- Full analysis set (FAS)
This patient set includes all patients in the SAF who had a baseline measurement for the primary endpoint. It will be the main analysis set for presentation of efficacy results. Treatment assignment will be as randomized.
- Full analysis set including completers (FAS-C)
This analysis set includes all patients in the FAS who completed double-blind treatment, i.e., did not prematurely discontinue treatment up to (and including) Week 12.
- Pharmacokinetic parameter set (PKS)
This patient set includes all patients in the SAF who provide at least one evaluable observation for the BI 655130 concentration, which was not flagged for exclusion. This patient set will be used for the display of concentrations.

The discussion of all exceptional cases and problems and the decisions on the allocation of patients to populations will be made at latest at the DBLM.

Handling of Treatment Misallocations in Analysis Sets

If a patient was administered incorrect treatment during the study, then for safety the following will be used in addition:

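### The EASI50 and EASI75 logistic models omit baseline EASI, which the primary MMRM uses; this may cost some precision and leaves chance baseline imbalance unadjusted

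*SAP*

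**What the plan says.** For the two EASI responder endpoints at Weeks 4 and 16, Protocol 7.3.2 states: "A logistic regression model will be used to predict the response rates and to calculate the risk difference for BI 655130 versus placebo". It names no covariates. SAP 7.5.2.1 fills that in: the endpoints are "analysed with a logistic regression model including treatment and Asian/Non-Asian as explanatory variables". The sensitivity analysis is a CMH test adjusted for the same stratum.

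The primary MMRM (SAP 7.4.1) models percent change in EASI and includes "the fixed continuous effects of baseline-by-visit interaction". The responder endpoints are that same percent change cut at a threshold (SAP 5.2.2): "Achieving a response of xx% or larger decrease from baseline in EASI score is denoted as EASIxx".

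Baseline EASI is never missing in the efficacy population. SAP 6.3 defines the full analysis set (FAS) thus: "This patient set includes all patients in the SAF who had a baseline measurement for the primary endpoint". On size, the Protocol synopsis states: "Approximately 45 patients will be entered in the study", with 30 on active and 15 on placebo. Randomisation is stratified by race and not by severity (Protocol 7.6).

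**The concern.** The plan treats baseline EASI as worth adjusting for when percent change is analysed as a continuous outcome, then drops it when the same quantity is dichotomised. The visible text of neither document gives a reason.

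Two things are at stake. If baseline severity predicts percent improvement, adjusting for it narrows the interval for the risk difference without collecting anything new. And with 15 placebo patients and no balancing on severity, a chance difference between arms is quite likely, and the planned model does nothing about it. The same SAP paragraph also leaves open how a risk difference is to be derived from a logistic model, and shows no rule for sparse responders.

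**Working it through.** **1. The plan's own figure.** Protocol 7.7 uses delta 25, SD 30, two-sided alpha 10%, power 80% and 2:1 allocation. Placebo n = (1 + 1/2) × (1.645 + 0.842)² × (30/25)² = 1.5 × 6.18 × 1.44 = 13.4, rounded up to 14. With 28 active, the total is 42, as the Protocol states (power 80.4% by noncentral t). This concerns mean percent change. No sample size, power or response rate is given for EASI50 or EASI75.

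**2. Chance imbalance.** The standard error of the baseline mean difference is √(1/30 + 1/15) = 0.316 SD. An imbalance of at least half an SD has z = 0.5/0.316 = 1.58, so it occurs in about 11% of such trials.

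Its effect depends on the correlation rho between baseline EASI and percent improvement. Assume mean improvements of 55 (active) and 30 (placebo), with SD 30. A half-SD imbalance moves the mean difference by rho × 0.5 × 30, which is 3, 4.5 or 6.75 points at rho 0.2, 0.3 or 0.45. Near the 50% cut the normal density is 0.393/30 = 0.0131 per point (active) and 0.319/30 = 0.0106 (placebo), on average about 0.0119. The EASI50 risk difference therefore moves by roughly 4, 5 or 8 percentage points. At rho = 0 it does not move.

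**3. Precision.** Trials of 30 versus 15 patients were simulated with SD 30 and delta 25 from the Protocol, and the risk difference was obtained by averaging predicted risks over the sample. Two set-ups were used:
- Set-up A: maximum likelihood, assumed placebo mean 35, 30% Asian, 6,000 to 10,000 trials per setting, stable fits only.
- Set-up B: Firth's penalised likelihood, assumed means 55 and 30.

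Variance of the risk difference with baseline EASI added, relative to the planned covariates:

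| rho (assumed) | EASI50, A | EASI50, B | EASI75, A | EASI75, B |
|---|---|---|---|---|
| 0 | 1.02 | 1.01 | 1.03 | 1.03 |
| 0.2 | 0.99 | 0.97 | 1.03 | 1.01 |
| 0.3 | 0.96 | 0.96 | 0.99 | 0.98 |
| 0.45 | – | 0.89 | – | 0.94 |
| 0.5 | 0.87 | – | 0.92 | – |

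In set-up A the break-even is at rho of about 0.2 for EASI50 and 0.2 to 0.3 for EASI75. For EASI50, a ratio of 0.96 narrows the interval by 1 − √0.96 = 2% and is worth 45 × (1/0.96 − 1) = about 2 patients. A ratio of 0.89 narrows it by 1 − √0.89 = 6%. EASI50 power at two-sided 10% (set-up A) goes from 66.5% to 66.1% at rho 0, from 66.0% to 68.0% at 0.3, and from 64.2% to 69.5% at 0.5.

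**4. Sparse responders.** At an assumed placebo mean of 30, the placebo EASI75 rate is 1 − Φ(45/30) = 6.7%, or 15 × 0.067 = 1.0 patient. The active rate is 1 − Φ(20/30) = 25.2%, or 7.6 patients. That is about 9 responders in the whole trial. At an assumed placebo mean of 35 the placebo rate is 9.1%, and the chance of no placebo responder is 0.909^15 = 24%. In line with this, about 26% of simulated EASI75 analyses in set-up A had no stable maximum-likelihood fit, with or without baseline.

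**5. Cost of penalisation.** Under set-up B's assumptions, Firth's method with averaged risks raised the placebo EASI75 rate from a true 6.7% to about 10%. It shrank the risk difference by about 1.5 to 2 points for EASI75 and 2 to 3 points for EASI50. This occurred with or without baseline. Mean squared error was still no worse than with raw proportions.

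**The case against.** The strongest objection is that a percent decrease is already scaled by baseline, in a population cut off from below: "Eczema Area and Severity Index (EASI) of at least 12 at screening and at least 16 at baseline". A strong correlation on the absolute score need not carry over to percent change, and having baseline in the MMRM does not prove that it is prognostic. This stands, and it is why the precision claim must be conditional. Three stronger readings are tempting, and the documents support none of them:
- **That the omission necessarily loses precision.** At rho below about 0.2 the extra parameter costs slightly more than it returns.
- **That imbalance passes in full into the risk difference.** It passes in proportion to prognostic strength, which is unknown. Randomisation protects the comparison on average, and adjustment accounts for imbalance rather than removing it.
- **That EASI75 would gain materially.** Its gain is negligible up to rho 0.3.

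It is also true that the efficacy analyses are exploratory (SAP 7), that baseline-adjusted inference on EASI is already provided by the MMRM at Weeks 4 and 16, and that the logistic model and the CMH test use the same stratum. Parts of the SAP are redacted, 7.4.2 among them, so a baseline-adjusted supplementary analysis cannot be excluded. These points keep the matter minor. They do not explain why the stated model for these endpoints omits a covariate that the plan uses for the same percent change.

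**Conclusion.** The omission is confirmed in the visible text, and the consequence is possible rather than certain. For EASI50, adding baseline EASI would change the variance of the risk difference by about +1% to +2% at correlation 0, -4% at 0.3 and -11% at 0.45. For EASI75 the figures are about +3%, -1% to -2%, and -6%. The worst case, a baseline that is not prognostic, costs at most about 3% of variance.

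These figures rest on normally distributed percent improvement, the Protocol's SD and delta, assumed placebo means of 30 to 35, and a correlation that the documents do not give. The Protocol and SAP do not contradict each other here, and the planned model is valid. This is an inexpensive improvement to a secondary analysis, worth having mainly for EASI50 and for consistency with the primary model.

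**What to change.** In SAP 7.5.2.1:
- Add baseline EASI as a continuous covariate to the EASI50 model at Weeks 4 and 16. Add it to the EASI75 model for consistency, with little gain expected.
- State that the risk difference is obtained by averaging predicted risks under each treatment over all FAS patients.
- Specify Firth's penalisation where responders are sparse or separation occurs, and note that it shrinks the risk difference by about 1 to 3 points. Show the observed proportions beside it; SAP 6.6.2 already plans observed-data frequency tables.
- Keep the stratum-adjusted CMH test as the sensitivity analysis.
- If baseline is deliberately left out, give the reason.

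The cost is one model term and a few sentences. No new data are needed and no FAS patient is lost. Because Protocol 7.3.2 names no covariates, the change does not conflict with it. It should be fixed before unblinding for the Week 16 analysis.
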